11.2. Sample Size Considerations

Approximately 36 patients will be enrolled and randomized in the study. The primary efficacy analysis based on serum AAT levels, will be executed after all enrolled patients complete Week 16 visit and will evaluate the difference in mean percent change from baseline at Week 16 between each active dose group and the pooled placebo groups. Patients will be randomized in a 2:1 (active:placebo) ratio within each of the 3 dose cohorts. With 8 patients in each of the 3 active treatment dose groups and 12 patients in the pooled placebo group, the study has 99% global power to declare at least one treatment dose group as different from placebo, assuming the treatment difference from placebo of at least 70 percent points and using a one-sided 2.5% level of significance with Hochberg's step-up adjustment for multiplicity of testing. Furthermore, the study has 97% conjunctive power to detect all dose groups that are truly different from placebo and 99% disjunctive power to detect at least one dose group that is truly different from placebo. The estimate of variability of the primary endpoint is calculated from prior studies to be 35%.

11.3. Randomization and Stratification

Following Screening, eligible patients will be randomly allocated in a 2:1 ratio within each dose cohort, to receive one of 3 dose levels of fazirsiran (25, 100, or 200 mg) or placebo. Randomization will be performed within each dose cohort to maintain blinding due to different dose volumes in the double-blinded phase.

Metabolic syndrome has been associated with increased risk of developing liver fibrosis in AATD (Clark et al., 2018). Randomization will be stratified by the presence of metabolic syndrome (defined as in Appendix 1) identified at Screening (Alberti et al., 2009). Randomization will also be stratified by presence of NASH (steatosis, inflammation, and ballooning) at Screening based on pre-dose study biopsy. Patients with both NASH and metabolic syndrome will be stratified based on the presence of NASH.

11.4. Screening Data

Demographics will be tabulated by patient and summarized by cohort and treatment group. Eligibility assessments at baseline, including medical/surgical history data and physical examination data (including height and weight), will be listed for each patient.

11.5. Safety/Tolerability Data

All safety analyses will be performed using the Safety Population. In general, safety analyses will be performed, and the results summarized by cohort and treatment group. All safety summaries will be accompanied by patient listings.

Treatment-emergent AEs will be summarized using the latest version of Medical Dictionary for Regulatory Activities (MedDRA) by System Organ Class (SOC) and Preferred Term (PT), classified from verbatim terms. The incidence and percentage of patients with at least 1 occurrence of a PT will be included, per the most severe grade using a 3-point scale (mild, moderate, severe). The number of events per PT will also be summarized. Causality (relationship to study treatment) will be summarized separately.

The incidence and frequency of AEs, SAEs, treatment-related AEs, treatment-related SAEs, and AEs leading to withdrawal, dose modification, or treatment discontinuation will be summarized by dose and treatment group per SOC and PT. AEs will also be summarized in listings. The duration of AEs will be determined and included in listings, along with the action taken and outcome.

The incidence of laboratory abnormalities will be summarized. Results for variables that are not coded will be presented in the listings as "below, within, and above" the normal limits of the laboratory. Pregnancy test results will be summarized separately by timepoint.

Vital sign measurements will be summarized at each scheduled timepoint using descriptive statistics. Physical examination findings will be summarized by timepoint and presented in patient listings.

ECG parameter changes overall, changes from baseline and qualitative assessments will be summarized.

Change from baseline in VC, FVC, FEV₁, and DLCO will be summarized by timepoint. For FEV₁, summary measures will include change from baseline expressed in mL, as a percentage of baseline value, and in units of percent predicted normal and will also be summarized as upper 95th percentiles with 95% confidence interval (CI). For DLCO summary measures will include change from baseline expressed as absolute change in values and as a percentage of baseline value. Number of patients requiring new initiation of augmentation therapy during the study and time from baseline until new initiation of augmentation therapy (Kaplan Meier analysis) will be evaluated.

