9.7. Safety Endpoints

The safety of fazirsiran will be evaluated by collection of the following measurements performed at specified timepoints:

- Monitoring of AEs/SAEs
- Physical examinations
- Vital signs
- ECG measurements
- Clinical laboratory tests (hematology, biochemistry, coagulation, urinalysis)
- Concomitant medications/therapy
- Reasons for treatment or study discontinuation due to toxicity
- Pulmonary Function Testing including spirometry (including VC, FVC, FEV₁, FEV₁/VC, and FEV₁/FVC), and DLCO. Changes in VC, FVC, FEV₁, and DLCO between patients receiving fazirsiran and patients receiving placebo will be analyzed and compared for statistical significance.
- The number of patients receiving fazirsiran versus placebo that require augmentation treatment at any time throughout the study will be summarized.
- Time until initiation of augmentation therapy in active versus placebo patients (Kaplan Meier)
- Number and severity of COPD exacerbations based on Global Initiative for Chronic Obstructive Lung Disease (GOLD) criteria in active versus placebo will be evaluated as an AE of special interest.

The AE/SAE reporting period for an enrolled patient will begin when the patient provides informed consent. Treatment-emergent AEs/SAEs will be those defined as following dose administration through EOS or Early Termination. All AEs/SAEs that occur during the AE reporting period specified in the protocol must be reported to Arrowhead Pharmaceuticals, Inc., regardless of the relationship of the AE to study treatment. Any known untoward event that occurs beyond the AE reporting period that the Investigator considers an SAE and possibly related to study treatment will be reported to Arrowhead.

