APPENDIX 3: PULMONARY FUNCTION MONITORING

Pulmonary function will be monitored closely throughout the AROAAT2001 study using spirometry, DLCO, periodic DSMB reviews, weekly Sponsor reviews and medical monitoring for pulmonary AEs.

If a patient in the AROAAT2001 study experiences an absolute decline of 10% or more in percent of predicted FEV₁ (must be confirmed on repeat within 30 days) from baseline with symptoms of chronic obstructive pulmonary disease (COPD) exacerbation,

OR experiences an absolute decline in percent of predicted FEV₁ by 10% (must be confirmed on repeat within 30 days) AND a decline in percent of predicted DLCO of at least 10%,

OR an absolute decline of percent of predicted FEV₁ of 20% or more (must be confirmed on repeat within 30 days), regardless of concurrent symptoms and regardless of any drop in percent of predicted DLCO,

they will be referred to a pulmonologist for possible initiation of augmentation therapy. Arrowhead will provide the therapy in any instance where the patient cannot access it through normal channels. Additionally, pulmonary monitoring visits for spirometry will be increased to approximately monthly.

If deemed necessary by the treating pulmonologist, AAT augmentation therapy may be initiated per locally approved package insert (typically weekly infusions at 60 mg/kg per dose) or equivalent for the duration of the AROAAT2001 study while the patient is on fazirsiran (or placebo) and for up to an additional 6 months after the patient's serum Z-AAT levels have returned to within 30% of their pre-dose Day 1 baseline serum AAT value OR until AAT levels have returned to within 30% of pre-dose Day 1 baseline and pulmonary function parameters (either DLCO or FEV1) have stabilized (defined as 2 sequential measurements that are not declining) OR until cessation of augmentation therapy is deemed appropriate by treating pulmonologist. In the circumstance of patients in the study newly started on AAT augmentation therapy, measurement of serum AAT may increase in frequency from SOA to monthly or every 2 weeks. This measurement may be done with a Z-AAT specific assay or may require occasional AAT augmentation washout for measurement of endogenous production using the clinical AAT assay. In countries where augmentation is not available or not reimbursed, the Sponsor will work to make therapy available as part of the AROAAT2001 clinical study.

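### The added FEV1 percentile summary (Section 11.5) sits in the tail of gains, not falls, and has no distribution-free 95% CI at these group sizes; count the falls by arm instead

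*Protocol*

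**What the plan says.** Section 11.5 (Safety/Tolerability Data) summarises FEV1 change from baseline by timepoint in three units: mL, percentage of baseline, and percent predicted. It adds that the change "will also be summarized as upper 95th percentiles with 95% confidence interval (CI"). It does not redefine change as size of decline, and it names no method for the interval.

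Section 9.7 (Safety Endpoints) says that changes in VC, FVC, FEV1 and DLCO in fazirsiran and placebo patients "will be analyzed and compared for statistical significance". No alpha, model, multiplicity rule or power is given for these tests.

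The direction of harm is clear elsewhere. Section 4.8 has the sponsor flag decreases of more than 10% from baseline each week. Appendix 3 acts when a patient "experiences an absolute decline of 10% or more in percent of predicted" FEV1, subject to further conditions.

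Group sizes come from Section 11.2: "With 8 patients in each of the 3 active treatment dose groups and 12 patients in the pooled placebo group".

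The SAP supplied is an addendum for the open-label phase. Its Section 6.4.6 adds summaries and plots of pulmonary function and otherwise defers to SAPv3.0.

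**The concern.** Less lung protection is the main theoretical risk of lowering AAT further in these patients, and the protocol builds much of its safety monitoring around it. A tail percentile is a sensible idea for such a risk, because a few patients may decline while the mean hardly moves. But the only tail percentile in the available plan is at the wrong end of a signed change. Moving it to the lower end would not rescue it, because groups this small carry very little information about a 5% tail.

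The tests in Section 9.7 raise a related point. They were not sized, so a non-significant result would leave open differences that might matter. What the data can exclude is shown by an interval, not by a p-value alone.

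**Working it through.** **Inputs.** Section 11.2: n = 8 per dose (24 active in all) and 12 pooled placebo. The documents give no SD for FEV1 change, so 5, 8, 10 and 15 percentage points are assumed below.

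**The plan's own power figure.** It concerns serum Z-AAT, not FEV1, and confirms the group sizes. It takes a difference of 70, an SD of 35 and one-sided 2.5%. For one dose against placebo, 70 / (35 × √(1/8 + 1/12)) = 2 / 0.4564 = 4.38, and Φ(4.38 − 1.96) = 99.2%. Simulating Hochberg's procedure over three doses with pooled variance gives 99.8% for at least one dose and 97.0% for all three. The protocol states 99% and 97%, so its figures are reproduced. No such figure is given for lung function.

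**Tail.** If change = follow-up minus baseline, a fall is negative. The upper 95th percentile is the value that only the top 5% of changes exceed, so it marks the largest gains.

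**Distribution-free interval.** An upper limit for the 95th percentile can be no higher than the sample maximum. The probability that the maximum reaches the true percentile is 1 − 0.95^n. By symmetry this is also the probability that the minimum reaches the true 5th percentile.

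| n | 1 − 0.95^n |
|---|---|
| 8 | 34% |
| 12 | 46% |
| 24 | 71% |
| 36 | 84% |

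For 95% one-sided, n ≥ ln 0.05 / ln 0.95 = 58.4, so 59. For a 97.5% upper limit, n ≥ ln 0.025 / ln 0.95 = 71.9, so 72. No group reaches this, nor do all 36 patients. Under the common (n+1)p rule the 95th percentile has rank 8.55 at n = 8 and 12.35 at n = 12. Both exceed n, so the point estimate is simply the maximum, which Section 11 already plans to report.

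**Normal-theory interval.** From the noncentral t, the 95% CI for the 95th percentile, in SDs above the sample mean, is:

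| n | Limits | Width |
|---|---|---|
| 8 | +0.85 to +3.64 | 2.8 SD |
| 12 | +0.97 to +3.02 | 2.1 SD |
| 24 | +1.14 to +2.46 | 1.3 SD |

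At n = 8, with an assumed SD of 5 to 15 points, the width is 2.79 × 5 = 14 to 2.79 × 15 = 42 points.

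**Significance tests.** Power of a two-sided 5% t-test for assumed SDs of 5 / 8 / 10 / 15 points:

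| True mean difference | 8 v 12 | 24 v 12 |
|---|---|---|
| 5 points | 55 / 25 / 18 / 10% | 78 / 40 / 28 / 15% |
| 10 points | 99 / 74 / 55 / 28% | ~100 / 93 / 78 / 45% |

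The difference detectable with 80% power is 1.35 SD (8 v 12) or 1.02 SD (24 v 12).

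**Counts instead.** With zero events the exact two-sided 95% upper limit is 1 − 0.025^(1/n): 37% for 0/8, 26% for 0/12 and 14% for 0/24. These intervals are wide, but they are valid at any n and need no assumption about the shape of the tail.

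**The case against.** The strongest reply is that this is one added line among many lung safety measures. That is correct. Section 11 gives the minimum and maximum for continuous variables, and Section 11.10 repeats this for safety parameters, so the worst FEV1 change in each group will be shown. Patient listings, new augmentation therapy with Kaplan-Meier time to it, COPD exacerbations as an event of special interest, weekly sponsor review, the individual rules in Appendix 3, and DSMB review of imbalances are all planned. A reader might infer that lung harm would go unseen, or that lung safety rests on this percentile. The documents do not support that.

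Three further replies also stand:

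- It would be too strong to say that no interval can be computed. A normal-theory one exists, and Section 11.5 does not exclude it. It is wide, though, and depends on the shape of a tail that 8 patients cannot check.
- It would be too strong to say that the tests lack power in general. Section 9.7 compares fazirsiran with placebo patients, which most naturally means 24 v 12, and without an FEV1 SD the power for a 10-point mean difference could be anything from 45% to about 100%. Nor do the documents say that non-significance will be taken as safety.
- SAPv3.0 may define the sign, the percentile method or threshold counts. It cannot be checked here.

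None of this answers the point about the percentile itself. Section 11.5 describes a signed change, and nothing in the available text turns it into a size of decline.

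**Conclusion.** The concern holds for one statistic. As Section 11.5 is written, the upper 95th percentile of FEV1 change describes gains, while harm is a fall. At 8, 12 or 24 patients it has no distribution-free 95% CI, and the lower 5th percentile would be no better. A normal-theory interval is possible but spans about 2.8 SD for a single dose group.

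The point on Section 9.7 is smaller. The tests were not sized, and a null result would not establish absence of harm. How weak they are depends on an FEV1 SD that the documents do not give.

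The conclusion assumes that change means follow-up minus baseline, that the groups are as planned in Section 11.2, and that SAPv3.0 does not already define these items otherwise. It is not a finding against the trial's lung monitoring.

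**What to change.** 1. In Section 11.5 and the matching SAP text, replace the upper-percentile summary. Report the number and proportion of patients whose percent-predicted FEV1 falls by at least 10 and at least 20 points from baseline, both for any fall and for falls confirmed on repeat. Give exact 95% CIs for each dose, pooled active and pooled placebo, in the blinded phase.
2. Label these as descriptive thresholds taken from Appendix 3. They are not its full referral criteria: the 10-point level there also needs confirmation within 30 days plus either COPD exacerbation symptoms or a DLCO fall of at least 10%, and the 20-point level also needs confirmation. The clinical rules stay as they are.
3. In Section 9.7, report mean differences in VC, FVC, FEV1 and DLCO with 95% CIs, beside or in place of the tests. State that a non-significant result does not establish absence of harm.
4. If a percentile is kept for any reason, state the sign of the change, the tail and the interval method.

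The cost is wording and table shells; the spirometry is already collected. The intervals will be wide. Besides the zero-event limits shown above, a 95% CI for a mean difference has a half-width of t × SD × √(1/n₁ + 1/n₂): 2.10 × 0.456 = 0.96 SD for 8 v 12 and 2.03 × 0.354 = 0.72 SD for 24 v 12. That width is a fair picture of what 36 patients can show.

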11.6. Immunogenicity Data

The number and percentage of patients who are ADA positive at baseline and at any post-baseline visit will be summarized. A listing of patients with positive ADA assay results will be provided.

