- Percent change in expression of liver fibrosis associated genes
- Percent change in *SERPINA1* messenger RNA (mRNA) levels
- Change in measures of fibrosis (Metavir fibrosis stage)
- Change in liver histology (e.g., globules, inflammation, steatosis)
- Measures of hepatic injury including ALT, GGT, and AST
- Change in MRI (where available and if feasible)
- Change in FibroScan® (where available)
- Serum fibrosis biomarkers (PRO-C3/PRO-C6), FIB-4, APRI

Pharmacokinetic Assessments:

Blood samples will be collected from all enrolled patients for sparse sampling plasma pharmacokinetic (PK) analysis after dose 1 (all patients) and 3 (fibrosis subset) per the SOA.

Immunogenicity Assessments:

Emergence of ADAs will be evaluated with samples drawn per the SOA.

Statistical Considerations: The objective of this Phase 2 study is to evaluate 3 dose levels relative to placebo and select a dose level to be used in the open-label phase of this study and in later stages of development based on the evaluation of safety, as well as percent change from baseline in serum Z-AAT levels. The primary efficacy analysis, executed after the last patient completes Week 16 visit, will evaluate the difference in mean percent change from baseline at Week 16 between each active dose group and the pooled placebo groups. The primary efficacy analysis, performed using the mixed model repeated measures (MMRM) approach, will be

executed in all randomized patients who receive at least one dose of study treatment (Full Analysis Set), regardless of the total number of received doses. With a total sample size of approximately 36, the study has 99% global power to declare at least one treatment dose group as different from placebo, assuming the treatment difference from placebo of at least 70 percent points (SD=35) and using a one-sided 2.5% level of significance with Hochberg's adjustment for multiplicity of testing. Details of planned statistical analysis will be provided in the statistical analysis plan (SAP).

Extended Efficacy Analysis will be performed after the last patient with fibrosis reaches the post-baseline biopsy visit. Patients will receive the treatment dose selected following the Week 16 Interim Analysis, only after the patient has completed the post-baseline biopsy visit (Week 48, 72, or 96). Final Analysis will be performed after all patients complete either an Early Termination or Study Completion visit and database lock.

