5.3. Secondary Endpoints

- Subject incidence of treatment-emergent AEs
- Absolute and percent change from baseline in total liver Z-AAT (insoluble + soluble) protein at post-dose biopsy visit
- Absolute and percent change from baseline in liver Z-AAT soluble protein at post-dose biopsy visit
- Absolute and percent change from baseline in liver Z-AAT insoluble protein at post-dose biopsy visit
- Absolute and percent change from baseline in liver function tests including ALT, aspartate aminotransferase (AST), alkaline phosphatase (ALP), gamma glutamyl transferase (GGT), total bilirubin, direct bilirubin, and international normalized ratio (INR) at Week 16 and over time through End of Study (EOS)
- Absolute and percent change in serum Z-AAT over time through EOS
- Change over time in PK measurements of fazirsiran at timepoints specified in the Schedule of Assessments (SOA)
- Incidence of anti-drug antibodies (ADAs) to fazirsiran
- Change from baseline in Metavir fibrosis stage at post-dose biopsy

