After all enrolled patients completed the Week 16 visit, an Interim Analysis was performed to select a single dose level (25, 100, or 200 mg) for the open-label phase of the study. Based on cumulative safety, efficacy, and PD data from the fazirsiran clinical program (clinical studies AROAAT1001, AROAAT2001, and AROAAT2002), a fazirsiran dose (200 mg) was selected

by the Sponsor. All patients with fibrosis at Screening who completed the post-dose biopsy visit at Week 48 (or Week 72 or 96) will receive fazirsiran at the selected dose for the duration of the study (open-label phase) but will remain blinded to their randomized treatment assignment.

Figure 1: Study Schema

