11. DATA ANALYSIS AND STATISTICAL CONSIDERATIONS

Statistical analyses and descriptive summaries will be presented for primary, secondary, and exploratory endpoints using appropriate methods. A detailed statistical analysis plan (SAP) will be provided. Descriptive statistics will be presented for all analyses unless otherwise specified. For continuous variables, data will be presented as number (n), mean, median, standard deviation, minimum, and maximum. Discrete variables will be presented as frequencies and proportions or percent. Data will be analyzed by cohort and treatment groups of fazirsiran 25, 100, and 200 mg versus pooled placebo. Data summarized in tables and figures will also be presented in patient listings.

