11.1. Study Populations

Four study populations will be defined and evaluated in this study.

- Safety Population: All patients who receive at least one dose of study drug. The Safety Population will be used for safety analyses. Patients will be included in the analyses according to the treatment they actually received.
- Full Analysis Set (FAS): All randomized patients who receive at least one dose of study drug. The FAS will be used to analyze endpoints related to efficacy. Patients will be included in the analyses according to the treatment planned by randomization.
- Modified Full Analysis Set (mFAS): All randomized patients who receive at least one dose of study drug who has pre-dose serum Z-AAT assessment and a Week 16 post-dose assessment.
- **PK population:** All FAS patients who have sufficient plasma concentration data to facilitate determination of PK parameters. Patients with major protocol violations will be assessed on a patient-by- patient basis for inclusion in the PK Analysis set. PK population will be used for PK analyses.

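### The planned ADA counts measure prevalence, not the incidence named as the secondary endpoint, and their post-baseline window has no stated end at the switch to open-label fazirsiran

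*Protocol*

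**What the plan says.** Protocol Section 5.3 lists the secondary endpoint as "Incidence of anti-drug antibodies (ADAs) to fazirsiran". The synopsis gives the aim in similar terms: "Emergence of ADAs will be evaluated with samples drawn per the SOA". Both describe new positivity.

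The analysis is in Protocol Section 11.6, which has two sentences: "The number and percentage of patients who are ADA positive at baseline and at any post-baseline visit will be summarized", and "A listing of patients with positive ADA assay results will be provided". It names no analysis set, treatment grouping or end of period, and it does not define an incident, induced or boosted case.

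The default grouping comes from the opening of Section 11: "Data will be analyzed by cohort and treatment groups of fazirsiran 25, 100, and 200 mg versus pooled placebo". On the later switch of treatment, Section 6.1 says: "All patients with fibrosis at Screening who completed the post-dose biopsy visit at Week 48 (or Week 72 or 96) will receive fazirsiran". This marks the start of the open-label phase, in which everyone still on study gets the dose chosen after the interim analysis. Table 2 schedules ADA samples before each 12-weekly dose through Week 196 and at Study Completion.

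The SAP addendum defines an Open-label Phase Set (Section 3.1) and resets baseline to the last value before the first open-label dose (Section 4). Its Section 6.1 says that open-label data are generally summarised apart from double-blind data. It has no ADA section, and it refers to SAPv3.0 for analyses already described there.

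**The concern.** Incidence requires knowing who was negative at the start and became positive. Section 11.6 asks only who was positive at each of two times. Pre-existing or non-specific reactivity present on Day 1 therefore reappears as a post-baseline positive with no drug effect. The protocol guards against this for adverse events: the treatment-emergent definition in Section 10.1 requires onset after dosing or worsening of a pre-existing condition. ADA has no such rule.

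The second gap is the open-ended window. A placebo patient whose first positive follows open-label fazirsiran, or a 25 mg or 100 mg patient whose first positive follows the move to the selected 200 mg dose, has a post-baseline positive in the sense of Section 11.6. Nothing in that section says to which group it belongs. At stake is whether the ADA table, a safety input to a dose-selection trial, shows what each randomised treatment induced.

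**Working it through.** The documents state no ADA rate, ADA sample size or ADA power, so there is no ADA figure to reproduce. The check is one of logic, followed by scale.

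**1. Two marginal counts do not give new cases.** Take a dose group of 8 and two possible sets of patients:

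| | Positive at baseline | Positive post-baseline | New converters |
|---|---|---|---|
| A: one patient positive before and after | 1/8 = 12.5% | 1/8 = 12.5% | 0 |
| B: one patient positive then negative throughout; another negative then positive | 1/8 = 12.5% | 1/8 = 12.5% | 1 |

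The planned table is the same in both cases, but the endpoint differs. If the sentence in Section 11.6 is instead read as patients positive at both times, the planned number excludes every new converter. Neither reading yields incidence.

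**2. Weight of one patient.** The group sizes in Section 11.2 are 8 per dose and 12 in pooled placebo. One patient is 1/8 = 12.5 points or 1/12 = 8.3 points.

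**3. Chance that such a patient is present.** Baseline positivity b is an assumption, shown from 2% to 10%. With independent patients, P(at least one) = 1 − (1 − b)^n.

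| b | n = 8 | n = 12 | n = 36 |
|---|---|---|---|
| 2% | 15% | 22% | 52% |
| 5% | 34% | 46% | 84% |
| 10% | 57% | 72% | 98% |

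For example, 1 − 0.95^36 = 0.842. These are chances of a baseline positive. The post-baseline count is inflated only if that patient is positive again later.

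**4. How far the window runs past the switch.** In Table 2 the scheduled post-baseline ADA samples for a patient with fibrosis who completes all doses are Week 4, Week 16, 15 visits from Week 28 to Week 196, and Study Completion: 1 + 1 + 15 + 1 = 18. This is a maximum, since dosing may stop earlier. With a Week 48 biopsy, and the first open-label dose at the next dosing visit (Week 52, sampled pre-dose), the samples before open-label exposure are Weeks 4, 16, 28, 40 and 52, which is 5. Up to 18 − 5 = 13 come after it.

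**5. Size if open-label positives were credited to placebo.** Only patients with fibrosis cross over. Section 7.1 requires at least 24 of 36, so at 2:1 about 24 × 1/3 = 8 placebo patients are expected at that minimum, and at most 12. With no baseline positives and an assumed induction rate q, the apparent placebo rate is (number crossing × q)/12. The low end is 8 × 0.05/12 = 3.3%; the high end is 12 × 0.20/12 = 20%. The double-blind phase alone would give 0%. This is conditional on a pooling that the documents do not state.

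**The case against.** A reader might infer that placebo patients first exposed in open label are counted as ADA cases of their randomised arm. The documents do not say so. Section 6.1 of the addendum states the opposite as a general rule and exempts no endpoint. The separate analysis set and reset baseline support it. For the Safety Population, Protocol Section 11.1 adds: "Patients will be included in the analyses according to the treatment they actually received". What remains is narrower: the rule is qualified as general, the addendum does not apply it to ADA, Section 11.6 does not name the Safety Population, and attribution by treatment received does not settle the case of a patient who receives two treatments in turn.

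SAPv3.0 may already define treatment-emergent ADA and a phase cut. The addendum deliberately does not repeat it, so its silence is not evidence of omission. This objection stands, and the request is conditional on it.

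The data may also be recoverable by hand, since baseline positives are counted, positives are listed and there are only about 36 patients. That softens the problem but does not remove it. Section 11.6 does not say that the listing shows negative or missing baseline results, and a secondary endpoint should not have to be rebuilt from a listing.

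Finally, the summary is descriptive, with no ADA test planned. Pre-existing positives fall on randomised arms by chance, and active and placebo patients with fibrosis share one sampling schedule. So no systematic bias towards one arm follows from the baseline problem. With 8 or 12 patients, however, a chance imbalance of one is visible in the percentages.

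**Conclusion.** The concern holds as a mismatch between endpoint and analysis. The counts in Section 11.6 are prevalence and cannot deliver incidence or emergence under either reading of the sentence. Each baseline-positive patient who stays positive adds 12.5 points to a dose group or 8.3 points to pooled placebo. The chance of at least one baseline positive in the trial is 52% to 98% over an assumed 2% to 10% range; that range is not from the documents.

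The open-label part holds only as an ambiguity. Positives after the switch could be credited to the randomised arm because no cut-off is stated for ADA, but the addendum's general rule points the other way. The 3.3% to 20% placebo figure applies only if that rule were not followed. Patients without fibrosis never enter the open-label phase and are unaffected.

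Nothing here touches the primary endpoint or its power. The change is worth making because the better measure uses samples already scheduled.

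**What to change.** First check SAPv3.0. If it already defines treatment-emergent ADA and a phase cut, cite it and align Section 11.6. Otherwise:

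- Define treatment-emergent ADA as negative at baseline and positive later, or a stated rise in titre from baseline if titres are available. Use patients with a baseline ADA result, and at least one later result, as the denominator, and report how many lack one.
- End the by-arm ADA window at the first open-label dose, with the pre-dose sample of that day as the last one counted.
- Add an open-label ADA table to the SAP addendum, by prior treatment (each fazirsiran dose, placebo), using the reset baseline in its Section 4.
- Keep the existing baseline and post-baseline counts alongside, and state that they are two separate counts.

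The cost is one definition and one extra table. No new samples or visits are needed.
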